## **PROTOCOL SYNOPSIS**

Title	Study on avatrombopag for the promotion of platelet engraftment after allo-HSCT
---------------------	---------------------------------------------------------------------------------

Version	1.0
Population	Patients with thrombocytopenia after allogenic hematopoietic stem cell transplantation (Allo-HSCT)
Objective	To evaluate the efficacy and safety of avatrombopag in the treatment of thrombocytopenia after Allo-HSCT, and provide evidence-based instruction of avatrombopag in promoting hematopoietic function reconstruction and reducing PLT transfusion for patients with delayed PLT reconstruction after Allo-HSCT in clinical practice
Design	Single, prospective, randomized controlled trial
Subject Number	78 participants
Eligibility Criteria	
Inclusion criteria
 
Each participant must meet all of the following criteria:
 
 
1. Male or female, aged between 18-60 years;
 
2. PLT has not been reconstructed 14 days after Allo-HSCT (PLT reconstruction was defined as the status of peripheral PLT count <math>> 20 \times 10^9/L</math> for consecutive 7 days without the need for PLT transfusion);
 
3. Expected survival time <math>> 3</math> months;
 
4. ECOG performance status 0-2;
 
5. Agree to receive the treatment of avatrombopag after Allo-HSCT and must sign the informed consent form.
 
 
Exclusion criteria
 
Participant meets any of the following criteria will be excluded from this study:
 
 
1. Pregnant or lactating;
 
2. With severe and uncontrollable infection;
 
3. With graft-versus-host disease (GVHD) with steroid
 

resistance;

4. With thrombotic microangiopathy;
5. With active thromboembolism requiring anticoagulation
6. With detected disease recurrence due to chimerism by flow cytometry;
7. With chronic active hepatitis B and C virus infection;
8. With secondary or multiple transplantation, or multiple organ transplantation;
9. With severe heart disease, lung disease, diabetes and metabolic diseases;
10. HIV positive;
11. With a history of PLT dysfunction or bleeding disorders

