
Statistical Analysis
	
 
• The sponsor will utilize appropriately qualified individuals to supervise the conduct of the trial to make sure the data collection, entry and management are in accordance with good clinical practice (GCP);
 
• Corresponding database will be established and source data will be input independently;
 
• Data administrator uses Epidata software to compile data entry program and carry out following process. Two data administrators will independently enter and proofread the data in double copies to ensure the accuracy.
 
 
Sample size estimation
 
 
• 78 participants
 
 
Based on the known literature, 35% of patients in the control group and 60% of patient in the trial group were

estimated to achieve the primary endpoint. Under the condition of the number ratio of control to trial group 1:1,  $\alpha=0.05$  (bilateral) and  $1-\beta=0.9$ , the number of participants in the control group and the test group was 79 and 79 respectively, calculated by the pros and cons test method of the clinical controlled study with PASS software. Further taking into account a 20% shedding rate per group, 95 cases per group were actually needed, for a total of 190 cases

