#### **Statistical analysis method**

- PLT and other mean variation trends were processed by repeated measurement data analysis of variance; Kaplan-Meier survival analysis was used to estimate the recovery of PLT count, cumulative predicted survival rate, cumulative recurrence rate of malignant hematologic disease, cumulative mortality associated with transplantation, and cumulative incidence of GVHD, and log-rank test was performed. Independent sample nonparametric test was used to analyze the accumulative demand of PLT suspension. The statistical process and graph were all run on SPSS 13.0 software. All tests were bilateral, and  $P \leq 0.05$  was considered to be significant. The PLT recovery time, granulocyte implantation time and PLT infusion number were compared by one-way analysis of variance. OS and DFS are estimated by Kaplan-Meier method. Risk factor analysis: variables: age, sex, HLA match, CD34+ cell number, incidence of GVHD within 100 days after transplantation, CMV infection rate. Multivariate Cox regression analysis was performed on the factors with significant differences ( $P < 0.05$ ) by one-way analysis of variance.

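### The stated total of 78 participants conflicts with the plan's own 90%-power calculation, which calls for 190 (198 with correct drop-out inflation); 78 gives about 60% power, or about 50% after 20% loss.

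*Combined protocol and SAP*

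**What the plan says.** The Protocol Synopsis, under Subject Number, gives "78 participants". The Sample size estimation part of the Statistical Analysis section opens with the same total.

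The paragraph directly below that bullet gives the justification. For the share of patients reaching the primary endpoint it assumes "35% of patients in the control group and 60% of patient in the trial group were" expected to respond. It takes a "number ratio of control to trial group 1:1", a two-sided alpha of 0.05 and power of 0.9. From these it reports that "the number of participants in the control group and the test group was 79 and 79 respectively". It then allows for drop-out and ends: "Further taking into account a 20% shedding rate per group, 95 cases per group were actually needed, for a total of 190 cases".

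The Statistical analysis method section confirms that "All tests were bilateral", but names no test for the binary primary endpoint.

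**The concern.** A trial cannot have both 78 and 190 as its total. The figure 79 is the size of one group, so a total of 78 falls below half of what the plan says it needs even before drop-out. An ethics committee, an investigator or a later reader cannot tell which trial is being run.

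The only power figure in the plan is 90%, and it sits under a bullet that says 78. If 78 patients are enrolled, a true 25-point benefit would be missed about four times in ten, or about half the time after 20% loss. A non-significant result could then be read as evidence of no benefit from a trial thought to have 90% power.

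**Working it through.** **Inputs**, all from Sample size estimation unless noted: control 35%, avatrombopag 60%, difference 0.25; two-sided alpha 0.05 (z = 1.960); power 0.90 (z = 1.2816); 1:1 allocation; 20% loss per group; headline total 78 (also in the Synopsis), which is 39 per group.

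**1. Reproduce the plan's 79.** Two-proportion z-test with unpooled variance:

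n = (1.960 + 1.2816)² × (0.35 × 0.65 + 0.60 × 0.40) / 0.25² = 10.507 × 0.4675 / 0.0625 = 78.6, so **79 per group**.

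This matches the document exactly. The pooled-variance version gives 82. The inputs have therefore been read correctly, and 79 is a per-group number: 2 × 79 = 158 evaluable patients.

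**2. Look for a derivation of 78 in total.** None of the variants tried gives 39 per group. The least demanding, one-sided at 80% power, still needs 47 (unpooled) to 49 (pooled) per group before drop-out.

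**3. The drop-out step.** The plan's 95 is 79 × 1.2 = 94.8, rounded up. Losing 20% of 95 leaves 95 × 0.8 = 76, which is short of 79. The correct step is 79 / 0.8 = 98.75, so 99 per group and 198 in total. With 76 evaluable per group, power is 87.8% (pooled) to 89.0% (unpooled), so this slip is small.

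**4. Power for 35% versus 60% if 78 is the real total.**

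- Unpooled: power = Φ(0.25 / √(0.4675/n) − 1.960). At n = 39: Φ(2.283 − 1.960) = Φ(0.323) = 62.7%.
- Pooled: power = Φ([0.25 − 1.960 × √(2 × 0.475 × 0.525/n)] / √(0.4675/n)). At n = 39: Φ((0.25 − 0.2217)/0.1095) = 60.2%.
- Losing 20% of 78 leaves 62.4 patients, or about 31 per group.

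| Evaluable per group | Pooled z | Unpooled z | Exact enumeration, chi-square | Exact enumeration, Fisher |
|---|---|---|---|---|
| 39 | 60.2% | 62.7% | 61.9% | 52.7% |
| 31 | 50.5% | 53.0% | 53.1% | 42.6% |

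**5. What 78 patients could detect.** With 35% in control, 90% power at 39 per group needs a rate of about 71% in the avatrombopag group (pooled) or 69.5% (unpooled). At 31 per group it needs about 75% (pooled) or 73% (unpooled). The plan assumes 60%.

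**6. Precision.** The 95% confidence interval for the difference has a half-width of 1.960 × √(0.4675/n). That is 0.215 at 39 per group, against 0.151 at 79.

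**The case against.** The strongest reply is that the documents do not show which total governs. The same section that opens with 78 also says that 190 were needed, and it ties 90% power to 79 per group, never expressly to 78. That is fair: the certain defect is the pair of incompatible totals, and the low power follows only if 78 is the target. Since 78 is the total stated in both places where a total is announced, that case has to be addressed. Reading 78 as a per-group figure has no support in the text and would still clash with 79, 95 and 190.

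Three smaller points also stand, without changing the conclusion:

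- The pooled formula is slightly less favourable than the unpooled one that reproduces 79. The gap is about 2.5 percentage points of power.
- With no test named for the primary endpoint, power at 39 per group can be given only as a range, 53% to 63%.
- The post-loss figures assume that all of the 20% drop out of the primary analysis. The full analysis set keeps anyone with one dose and an efficacy evaluation, so some patients who withdraw later may still count. The 50% is a scenario built on the plan's own allowance.

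It is also right that the inflation slip is minor: 8 patients in total and about one point of power.

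**Conclusion.** The concern holds. The plan gives two totals, 78 and 190, that cannot both be right, and its calculation supports neither 78 nor, strictly, 190: correct inflation gives 198. If 78 is the real size, power for the assumed 25-point difference is about 60% (53% to 63% depending on the test) with no losses. It is about 50% (43% to 53%) if 20% of patients are lost to the primary analysis. These figures rest on the plan's own response rates, two-sided alpha of 0.05 and equal allocation. Total sample size is a basic design parameter, so this must be fixed.

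**What to change.** Use one total in the Synopsis and in Sample size estimation, and name the test for the primary endpoint so that the power figure is tied to it.

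**If 78 is the real size:** remove the implication that it comes from the 90%-power calculation. Suggested wording, assuming a z-test or chi-square test: 78 participants (39 per group) give about 60% power for 35% versus 60%, and about 50% if 20% are lost; 90% power applies only to a difference of about 35% versus 71%. If Fisher's exact test is chosen, the first two figures become about 53% and 43%, and the detectable rate must be recomputed. Add that a non-significant result would not show that the treatments are equivalent. This costs wording only and no extra patients, though the stated power becomes less favourable.

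**If the calculation governs:** replace 78 in both places and correct 95/190 to 99/198 (79 / 0.8). If enrolment has been planned for 78, this means 198 − 78 = 120 more patients.

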**Statistical analysis data set**

- **Full analysis set (FAS):** All subjects who were enrolled and had at least one dose of investigation product along with efficacy evaluation were included in FAS as per the intention-to-treat (ITT) principles. FAS contributes to the main population for efficacy evaluation in this study.
- **Per-protocol set (PPS):** PPS includes all subjects who have fulfilled the protocol-required treatment or have not seriously violated the protocol. The exact definition of serious violation will be finalized during data review, which includes but not limited to the following conditions: fails to meet the main inclusion criteria, experiences the treatment that significantly interferes with efficacy evaluation after enrollment, poor compliance, poor follow-up record that significantly beyond the time window. PPS contributes to the secondary population for efficacy evaluation in this study. However, if the analysis results of PPS are inconsistent with the FAS, detailed analysis of the inconsistent results is required.

- **Safety set (SS):** SS is defined as the data that collected from subjects receiving at least one dose of investigation product.

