**Withdrawal criteria**

1. PLT remains less than  $20 \times 10^9/L$  after two weeks' treatment of avatrombopag in a maximum dose of 60

	
mg/d (Solution: receive other treatment after withdrawal from the study);
 
 
2. The participant or his legal guardian requests a withdrawal ;
 
3. c poor compliance(medicine taken less than 80% of the prescribed amount or more than 120% of the prescribed amount);
 
4. With requirement of a medicine that is prohibited in the study;
 
5. With adverse events that discontinues the study;
 
6. With some unexplained serious complications;
 
7. Be pregnant during treatment;
 
8. Deemed unsuitable for further study by the investigator.
 
 
Trial Termination
 
 
1. Sponsor decides to stop the trial for safety reasons;
 
2. Independent ethics committee decides to stop the trial;
 
3. Principal investigator decides to stop the trial.
 

Investigational Product
	
 
• Name: avatrombopag;
 
• Dosage form: tablet;
 
• Specification: 20 mg/tablet.
 

Treatment Design
	
 
• The whole study is divided into two stages, including 4-weeks' core study and 4-weeks' extended study;
 
• During the core study, participants are randomly assigned into the avatrombopag group and the rhTPO treatment group(standard group) with 1:1 ratio. The initial dose of avatrombopag is 20 mg/d. If the patient's PLT count remains less than <math>20 \times 10^9/L</math> after one week, the maximum dose was increased to 40 mg/d.
 
 
Avatrombopag will be taken orally with food. The rhTPO

will be subcutaneously injected with dosage of 300 U/kg/d;

- After the end of the core study, participants in the avatrombopag group who does not meet the withdrawal indication can be enrolled in the extended study and continue the avatrombopag treatment with a maximum dose of 60 mg/d. Participants who does not respond to treatment in the rhTPO group (PLT < 20\*10^9/L ) can also be enrolled in the extended study to receive avatrombopag treatment, by titrating avatrombopag in the dose of 20-60 mg/d according to the participants' condition;

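### The per-protocol set is joined by 'or', so read literally it keeps serious violators who completed treatment and weakens the comparison with the FAS

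*Combined protocol and SAP*

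**What the plan says.** All of this is in the combined protocol and SAP.

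- **Membership rule** (Statistical analysis data set, PPS): "PPS includes all subjects who have fulfilled the protocol-required treatment or have not seriously violated the protocol".
- **Definition of a serious violation** (same paragraph): "The exact definition of serious violation will be finalized during data review". Four kinds are named in advance in an open-ended list, "which includes but not limited to the following conditions: fails to meet the main inclusion criteria", followed by treatment that interferes with efficacy evaluation, poor compliance, and follow-up well outside the visit window.
- **Role of the sets** (same section): "FAS contributes to the main population for efficacy evaluation in this study". The PPS is the secondary efficacy population, and a disagreement between the two has to be looked into in detail.
- **Related withdrawal rules** (Withdrawal criteria): participants are withdrawn for "poor compliance(medicine taken less than 80% of the prescribed amount or more than 120% of the prescribed amount", or when they need a medicine the study prohibits. The PPS paragraph does not cite these rules.
- **Masking** (Design; Treatment Design): the design is given as "Single, prospective, randomized controlled trial". For one arm, "Avatrombopag will be taken orally with food"; the other drug "will be subcutaneously injected with dosage of 300 U/kg/d". No masking, placebo or dummy is described, and nothing says when data review takes place relative to results by arm.

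**The concern.** A per-protocol set normally needs both conditions: the participant received the required treatment and had no serious violation. With *or*, the set is the union of the two groups instead of their overlap. The list of serious violations then has no effect on anyone who completed treatment, which contradicts the evident purpose of listing them.

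What is at stake is the second efficacy population and the one use the plan makes of it, the consistency check against the FAS. The more violators the PPS retains, the closer it lies to the FAS and the less an agreement between the two says about robustness. There is also a practical risk. A programmer who follows the text builds the wrong set, while an analyst who silently reads *or* as *and* is choosing a population that the plan did not specify.

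**Working it through.** The documents give no figure for the PPS, so there is none to reproduce. The check is one of logic, followed by a range on assumed rates.

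**Step 1. The rule in each case.** Let C = completed required treatment and V = serious violation.

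| C | V | As written: C or not V | With *and*: C and not V |
|---|---|---|---|
| yes | no | in | in |
| yes | yes | **in** | out |
| no | no | in | out |
| no | yes | out | out |

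As written, one cell of four is excluded. With *and*, one cell of four is kept. The defect is the second row. The third row matters for the fix.

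**Step 2. Which named violations can reach the second row.** Set the PPS list beside Withdrawal criteria and Concomitant Treatment:

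- *Main inclusion criterion not met.* No withdrawal criterion specifically covers this. Such a participant can complete and stay in.
- *Follow-up far outside the window.* The same applies.
- *Interfering treatment.* Need of a prohibited medicine, such as another TPO-RA, leads to withdrawal. Those participants would normally fail both conditions and be excluded even under *or*. Interfering treatment that is not prohibited leaves the participant in.
- *Poor compliance.* The 80%/120% withdrawal criterion normally makes these participants non-completers, so they too are excluded under *or*.

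The literal rule therefore retains mainly the first two groups and part of the third.

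**Step 3. Size, on assumptions.** Let c = share completing, v = share with a serious violation, and N = 78 (the stated subject number; the sample-size paragraph arrives at 190, for which counts scale by 190/78). Violators kept under *or* = N × P(C and V). This lies between N × max(0, c + v − 1) and N × min(c, v), and equals N × c × v if C and V are independent.

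- c = 0.80, v = 0.10: lower limit 78 × 0 = 0; independence 78 × 0.80 × 0.10 = 6.2; upper limit 78 × 0.10 = 7.8.
- c from 0.70 to 0.90, v from 0.05 to 0.20: independence gives 78 × 0.70 × 0.05 = 2.7 to 78 × 0.90 × 0.20 = 14.0. With any degree of association the range is 0 to 78 × 0.20 = 15.6.

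Step 2 shows that violation and non-completion tend to go together, so the independence values are probably too high.

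**Step 4. Why *and* alone is not enough.** It also removes the third row: non-completers without a violation, N × [1 − c − v + P(C and V)]. At c = 0.80, v = 0.10 this is 78 × 0.10 = 7.8 if no violator completes, and 78 × 0.20 = 15.6 if all do (independence: 78 × 0.20 × 0.90 = 14.0). Some of these may have stopped because the protocol told them to: reconstruction sends participants to follow-up (Study process), a sufficient count leads to taper (Treatment Design), and persistent non-response leads to withdrawal (Withdrawal criteria). Removing the last group would take treatment failures out of the set.

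**The case against.** The strongest reply is that *or* is a drafting or translation slip. The paragraph goes straight on to list serious violations, which makes sense only if they exclude. That is likely, and it supports correcting the word, since the text as it stands directs a different set. It is also true that the FAS carries the main efficacy result and that no decision rule depends on the PPS; a discrepancy only calls for closer analysis. Both points limit the weight of the matter without removing it.

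Three stronger readings are tempting, and the documents do not support them.

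- A reader might infer that the PPS must be almost identical to the FAS, so that the consistency check can never fail. That needs violation and completion to be unrelated. The withdrawal rules for compliance and prohibited medicines link them, so some violators are excluded even under *or*. The check is weakened, not abolished.
- A reader might infer that the violation list will be written by people who see arm and outcome. Tablet against injection with no dummy makes visible assignment a reasonable inference, but masking is simply not mentioned, and the plan does not say who conducts data review or what they see. Settling violations at data review is ordinary practice; what is missing is its timing and a safeguard.
- A reader might infer that the list is blank until then. Four categories are named, and one has a numerical limit elsewhere in the protocol, though as a withdrawal criterion.

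**Conclusion.** The point holds as a defect of wording with a real but limited consequence. Read literally, the rule keeps serious violators who completed treatment, against the plan's own list of violations, and makes agreement between PPS and FAS less informative. This conclusion follows from the text and the truth table and needs no assumed rates.

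The size is not known. On the assumed rates above, 0 to about 16 of 78 participants would be wrongly retained, with the independence values (about 3 to 14) probably on the high side. The range rests on assumed completion and violation rates and on reading withdrawn participants as non-completers, which the plan implies but does not define. The open timing of data review is a secondary matter.

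**What to change.** 1. In the PPS definition, replace *or* by *and*.
2. Add one sentence: a participant who stopped study drug because the protocol directed it (reconstruction, taper, or withdrawal for non-response) counts as having completed the required treatment. This changes no clinical rule; it only stops *and* from removing treatment failures and early responders.
3. As a secondary safeguard, finalise the violation definitions and PPS membership before any result by arm is produced. Use listings with treatment assignment removed and compliance shown as a percentage of the prescribed amount, since tablets or units would reveal the arm. Show protocol-directed stopping as a yes/no item, because the non-response criterion is written for avatrombopag and naming it would also reveal the arm. Outcome cannot be fully hidden, because reasons for stopping carry information about response; the protection comes from hiding assignment and from the timing.

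Items 1 and 2 cost one word and one sentence. Item 3 costs more: the named categories need working definitions (which inclusion criteria are main ones, how far outside the window is too far), plus a recoded listing. No sample size or main analysis changes.

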- Patients who achieved PLT reconstruction during the core study and the extended study period are followed up to 4 weeks after investigational product withdrawal, and PLT count is measured for one time during the follow up;
- Adjustment Indication: When PLT ≥ 50\*10^9/L excluding the factor of blood transfusion, the dosage of avatrombopag and rhTPO will be eventually decreased and stopped according to clinicians.

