#### **Safety analysis**

- Safety and tolerance evaluation consist of adverse events and changes in laboratory values. Adverse

	
events were statistically described and listed in terms of occurrence, endurance, severity, relationship to the investigation product and outcome. Abnormalities in laboratory values were summarized in toxicity grade as per CTC AE 5.0. At the same time, the statistical description of the changes of the assessment values was carried out.

Study Duration
	
1.5 years

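### No cut-off separates adverse events before and after the rhTPO-to-avatrombopag switch, and the safety set and FAS are tied to a product listed as avatrombopag only

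*Combined protocol and SAP*

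**What the plan says.** - **Analysis sets.** Under Statistical analysis data set, the safety set reads: "SS is defined as the data that collected from subjects receiving at least one dose of investigation product". The FAS, which the plan ties to intention-to-treat and makes the main efficacy population, uses the same condition: "All subjects who were enrolled and had at least one dose of investigation product along with efficacy evaluation were included in FAS".
- **Product and arms.** The Investigational Product entry reads "Name: avatrombopag", a 20 mg tablet. rhTPO does not appear there. Under Treatment Design, "participants are randomly assigned into the avatrombopag group and the rhTPO treatment group(standard group) with 1:1 ratio".
- **Switch.** Treatment Design says that rhTPO participants without response, defined by a platelet count below 20×10⁹/L, "can also be enrolled in the extended study to receive avatrombopag treatment". It places this after the end of the four-week core study. The visit schedule under Study process instead lets standard-treatment non-responders enter the extended study after visit 3, which is day 28±2 after transplantation.
- **Adverse events.** Concomitant Treatment (item 7) has events observed in all participants at each visit, from consent to the end of the study. Safety analysis describes them by occurrence, duration, severity, "relationship to the investigation product and outcome". It does not mention treatment received, study period or the switch. Outcome Measure separates some efficacy endpoints by core and extended study; the safety measures carry no such separation.

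**The concern.** Two problems meet in the same definition.

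First, the dose condition in both sets refers to a product that the synopsis lists as avatrombopag alone. Taken word for word, an rhTPO patient who responds and never switches belongs to neither set, while an rhTPO non-responder who switches belongs to both.

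Second, and more important, counting rhTPO as a qualifying drug does not settle how events are attributed. The safety set takes the data of a dosed patient with no limit on period, and some rhTPO patients will have been exposed to both drugs. A table by randomised arm then puts avatrombopag-period events in the rhTPO column, which would make avatrombopag look relatively safer. A table by whether avatrombopag was ever received errs the other way and charges rhTPO-period events to avatrombopag. Safety is part of the stated objective, so the plan should fix the rule before the data are seen. The causality item has a related gap: for an event on rhTPO before any switch, the listed product is a drug the patient has not taken.

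**Working it through.** The plan gives no figure for this point. The only planning number used is the 35% control response under Sample size estimation.

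**1. The plan's own figure.** With 35% against 60%, two-sided alpha 0.05, power 0.90 and unpooled variance:

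n = (1.960 + 1.282)² × (0.35×0.65 + 0.60×0.40) / 0.25² = 10.51 × 0.4675 / 0.0625 = 78.6, so 79 per group, as stated. Then 79 × 1.2 = 94.8, so 95 per group and 190 in total. The synopsis also gives 78 participants (39 per arm at 1:1). That conflict is a separate matter and does not change the proportions below; both arm sizes are shown.

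**2. Share of the rhTPO arm that could carry post-switch events.** Assume that everyone who misses the endpoint is eligible and switches at the end of the core study: 1 − 0.35 = 0.65.
- 39 per arm: 0.65 × 39 = 25.4, about 25 patients.
- 95 per arm: 0.65 × 95 = 61.8, about 62 patients.

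This is a conditional upper bound. Switching is optional. Eligibility is a platelet count below 20×10⁹/L, whereas the endpoint is 7 consecutive transfusion-free days at or above that level, so the two groups need not coincide. If the switch can come after visit 3, some patients could switch who would otherwise have responded by week 4, and 65% would no longer be a strict ceiling.

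**3. Effect on an event percentage (illustration; risks assumed and independent between periods).** Let f be the share switching, r₁ the risk on rhTPO and r₂ the risk on avatrombopag after the switch. The rhTPO column shows (1 − f)·r₁ + f·[1 − (1 − r₁)(1 − r₂)]. Take r₁ = 10%, so the rhTPO-only value is 10%.

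| f | r₂ | Calculation | rhTPO column |
|---|---|---|---|
| 0.65 | 10% | 0.035 + 0.65×0.19 | 15.9% |
| 0.65 | 20% | 0.035 + 0.65×0.28 | 21.7% |
| 0.325 (half of them switch) | 10% | 0.0675 + 0.325×0.19 | 12.9% |
| 0.325 (half of them switch) | 20% | 0.0675 + 0.325×0.28 | 15.9% |

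The distortion does not need avatrombopag to be the riskier drug; added time at risk is enough.

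**4. Would a core/extended split separate the drugs?** Treatment starts at visit 1, day 15.
- Treatment Design: switch after four weeks, about day 15 + 28 = 43.
- Study process: switch after visit 3, day 28±2, that is 11 to 15 days into treatment (centrally 28 − 15 = 13).

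On the second timing, about 43 − 28 = 15 days of the nominal core period could be spent on avatrombopag by a patient randomised to rhTPO. A split by calendar period would leave those days in the rhTPO column. Only a cut at the individual switch date separates the drugs.

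**The case against.** The strongest reply is that the exclusion is a matter of wording. Treatment Design says that patients who achieve reconstruction in either stage, with no restriction to one arm, are "followed up to 4 weeks after investigational product withdrawal", and the next item tapers both drugs together. The FAS is labelled intention-to-treat, and the sample size assumes a 35% control response. This stands. A reader might infer that the plan drops all rhTPO responders, keeps only rhTPO failures and so fixes control response at 0%. The documents do not support that. It needs the narrowest reading of one term against the plan's other usage. Even then, 0% would not be assured, because a patient who switches after visit 3 could still reach the endpoint within the core period.

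The second reply is that nothing in the plan instructs anyone to pool events across the switch. Safety analysis is descriptive and silent on arm and period, so a table by treatment received would fit the text equally well, and the visit-by-visit records would allow it. This also stands in part: misattribution follows from a missing rule and is not prescribed. It does not remove the problem, because the one population that is defined has no period limit and the rule would otherwise be chosen after the events are known.

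**Conclusion.** The point holds in two parts of unequal weight. The dose condition in the safety set and FAS is a wording defect: as listed, the product is avatrombopag only, although both drugs were evidently meant. The substantive gap is that adverse events are collected to study end with no cut-off at the switch, so a by-arm summary of the safety set would count avatrombopag-period events in the rhTPO arm.

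The affected share of that arm is at most about 65%, if everyone missing the endpoint at the 35% planning rate is eligible and switches at the end of the core study. The actual share cannot be derived from the documents. The shift from 10% to between 12.9% and 21.7% is an illustration under assumed risks, not an estimate. A split by study stage alone would not cure the problem while the two statements of switch timing disagree.

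**What to change.** 1. Define the safety set as patients who received at least one dose of avatrombopag or rhTPO. Make the FAS dose condition refer to either study drug, with analysis by randomised arm.
2. Compare adverse events between arms only for onset from first dose to the earlier of the end of the core study or any switch, and give exposure time in each arm.
3. Tabulate events after a switch separately, as *avatrombopag after rhTPO*, with exposure time.
4. State which drug the causality assessment refers to in each period.
5. Reconcile the switch timing in Treatment Design with that in the visit schedule. Which timing applies is for the investigators to settle; the cut-off in item 2 works under either.

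The cost is a few lines of wording and one extra table, using event and medication records already collected at each visit. The price is shorter comparative safety follow-up, and shorter still in the rhTPO arm if switching can occur before the core study ends.
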